#### 2 STUDY OBJECTIVES AND ENDPOINTS

#### 2.1 OBJECTIVES

# 2.1.1 Primary Objective

The primary objective of this clinical study is to evaluate the safety and tolerability of Treprostinil Inhalation Powder (TreT) in subjects with PAH currently treated with Tyvaso®.

# 2.1.2 Secondary Objectives

A secondary objective of this clinical study is to evaluate systemic exposure and PK of treprostinil in subjects with PAH when delivered as Tyvaso and TreT. Additionally, this study will evaluate 6-Minute Walk Distance (6MWD) at study entry and after 3 weeks of treatment with TreT. The Optional Extension Phase of this study will evaluate long-term safety and tolerability of TreT in subjects with PAH previously treated with Tyvaso. Further, this study will evaluate subject satisfaction with and preference for inhaled treprostinil devices with the Preference Questionnaire for Inhaled Treprostinil Devices (PQ-ITD) and patient-reported PAH symptoms and impact with the Pulmonary Arterial Hypertension-Symptoms and Impact (PAH-SYMPACT®) Questionnaire.

# 2.2 ENDPOINTS

The following endpoints will be analyzed:

- PK assessments
- AEs
- Vital signs
- 12-lead electrocardiogram (ECG)
- Clinical laboratory assessments
- 6MWD
- PQ-ITD
- PAH-SYMPACT Questionnaire domain scores

#### 3 STUDY DESIGN

This is a Phase 1b safety and tolerability single-sequence study in which subjects on a stable regimen of Tyvaso will switch to a corresponding dose of TreT. At Baseline, subjects currently taking stable doses of Tyvaso (6 to 12 breaths 4 times daily [QID]) will take a dose of Tyvaso in the clinic and undergo PK assessments, safety assessments, and a 6-Minute Walk Test (6MWT). Following the in-clinic assessments, subjects will switch from Tyvaso to the corresponding dose of TreT and take their first dose of TreT in the clinic. Following 3 weeks of treatment with TreT, subjects will return to the clinic and receive 1 dose of TreT and undergo PK assessments, safety assessments, and a 6MWT as performed at the Baseline Visit.

Following the Week 3 Visit, subjects will be offered the opportunity to participate in the Optional Extension Phase of the study. Subjects who elect to discontinue TreT at the end of the Treatment Phase will return to the clinic in 2 weeks for an End of Study Visit. Subjects who elect to enter the Optional Extension Phase will remain on TreT and attend study visits every 8 weeks until the study is terminated or the drug/device becomes commercially available. If the subject discontinues TreT prematurely during the Optional Extension Phase, he/she must return to the clinic as soon as possible for an Early Termination Visit.

Screening Phase: Prospective subjects will be assessed during the Screening Phase to determine eligibility for the study. The Screening Visit must occur within 14 days prior to Baseline. During this Screening Phase, eligible subjects will sign the Informed Consent Form and undergo screening assessments. Subjects who satisfy all eligibility criteria during the Screening Phase may return to the clinic at Baseline for enrollment. If subjects are able to satisfy all eligibility criteria on the same day, a combined Screening/Baseline Visit may be conducted.

Treatment Phase: The Treatment Phase consists of 2 study visits to the clinic separated by 3 weeks of treatment with TreT. At Baseline, subjects will receive 1 dose of Tyvaso in the clinic and undergo PK assessments (at the following timepoints: 15 minutes before dose and 5, 10, 15, 30, 45, 90, 120, 180, 240, and 300 minutes after dose), safety assessments, and a 6MWT. No additional dose of Tyvaso will be administered, nor will TreT be started, until after the PK sampling assessment is complete. Following these assessments, subjects will be assigned a corresponding dose of TreT based upon their current stable Tyvaso dose and will receive the first dose of TreT in the clinic. Each subject will receive TreT QID by oral inhalation for 3 weeks. Following 3 weeks of treatment, subjects will return to the clinic and receive 1 dose of TreT in the clinic and undergo PK assessments, safety assessments, and a 6MWT as performed at the Baseline Visit. Questionnaires evaluating patient preference for inhaled treprostinil devices and patient-reported PAH symptoms and impact will also be administered. At each study visit, AEs will be assessed, vital signs will be recorded, and a physical examination, including oropharyngeal examination, will be performed. Following the Week 3 Visit, subjects may choose to participate in the Optional Extension Phase of the

study. If the subject does not elect to participate in the Optional Extension Phase of the study, he/she must discontinue TreT, may resume Tyvaso therapy, and must return to the clinic 2 weeks after TreT discontinuation for an End of Study Visit. Blood samples for an optional evaluation of change in biomarkers (specific targets to be determined) will be collected at the Baseline Visit and Week 3 Visit. An additional blood sample for an optional evaluation of whole genome sequence will be collected at the Baseline Visit.

Optional Extension Phase: The Optional Extension Phase will occur following completion of the Treatment Phase and continue with clinic visits every 8 weeks until the study is terminated for any reason or the drug/device becomes commercially available. To be eligible for the Optional Extension Phase, subjects must complete the Treatment Phase, elect to continue TreT, and agree to attend follow-up visits in the clinic. Dosing titration will be encouraged during the Optional Extension Phase; the dose of TreT should be titrated upward, as clinically tolerated, to identify a maximum stable dose in each subject. Subjects who discontinue TreT must complete an Early Termination Visit as soon as possible. A blood sample for an optional evaluation of change in biomarkers will be collected at the Week 51 Visit.

A study flow chart is available in Figure 3-1.

Screening Phase Treatment Phase Optional Extension Phase Follow-up Clinic Visits every 8 weeks continue Baselin e TreTWeek 3 (Tyva so dose, Screening seria1 (TreT dose and 1-14 days 3 weeks pharm acokinetic seria1 mav sampling, and pharm a cokinetic resume first dose of sam pling) Tvvaso TreT) 2 weeks End of Study

Figure 3-1 Study Flow Chart

#### 4 RANDOMIZATION

Subjects are not randomized. Subjects will be assigned treatment with TreT based on their current Tyvaso regimen as detailed in Table 4-1. An Interactive Response Technology (IRT)

will be utilized to assign each subject the appropriate study drug for the 3-week Treatment Phase and the Optional Extension Phase.

**Table 4-1** Treatment Assignments

Study Entry	Treatment Phase	
Tyvaso Dose (QID)	TreT Dose (QID)	Device Requirement
6 to 7 breaths	32 mcg	32 mcg cartridge
8 to 10 breaths	48 mcg	48 mcg cartridge
11 to 12 breaths	64 mcg	32 mcg + 32 mcg cartridges

Abbreviations: QID, four times daily; TreT, Treprostinil Inhalation Power.

#### 5 STRATIFICATION

No stratification will be done in this study.

# 6 SEQUENCE OF PLANNED ANALYSES

After all subjects complete the Treatment Phase, the Treatment Phase database will be locked and analysis of the data from the Treatment Phase will be carried out. Any available data from the Optional Extension Phase will also be analyzed at this time. At the completion of the study, final analyses of the Optional Extension Phase data will be conducted.

#### 7 SAMPLE SIZE CONSIDERATIONS

For this study, the total sample size is estimated to be 45 subjects and is not based on power calculations.

#### 8 ANALYSIS POPULATIONS

The Safety Population is defined as all subjects who received at least 1 dose of TreT during the Treatment Phase. All analyses will be performed on this Safety Population unless otherwise specified.

# 9 GENERAL CONSIDERATIONS FOR DATA ANALYSES

All the data collected in the electronic Case Report Form (eCRF) will be listed. In general, listings will be sorted by TreT dose, subject number, and scheduled assessment (if applicable). Listings will include assessment date, assessment time (if available), study day, and all relevant data collected in the eCRFs. For data collected on a fixed schedule, the

assessment identifier or the nominal time point will also be included on the listing. Repeat or redundant observations within an assessment window and observations that do not fall within any predefined assessment window (and will, therefore, be excluded from summaries) will be flagged in these listings. Subjects who are not included in the Safety Population will be flagged.

In general, the data will be summarized by scheduled assessment within each TreT dose and overall and separately for each phase. For continuous variables, summary statistics will include the mean, standard deviation, median, minimum, and maximum. For summaries of non-normal data such as 6MWD, interquartile range (lower quartile, upper quartile) may also be included. Minimums and maximums will be expressed using the level of precision in which the variable was collected. All other statistics will be rounded, using an additional decimal place than was collected. For discrete variables, summaries will include the frequency and percentage in each category. Percentages will be rounded to 1 decimal place. Whenever practical, categories of discrete variables will be ordered and labelled as they appear in the eCRF, and all categories represented on the eCRF will be included in summaries, even when they do not apply to any subjects in the study.

All statistical calculations will be completed using SAS® Version 9.4 or above.

#### 9.1 COVARIATES

There are no planned covariates.

#### 9.2 EXAMINATION OF SUBGROUPS

The following subgroup analyses will be performed if the data warrant:

- Background therapy (None, monotherapy, or 2 or more background medications)
- Background therapy (endothelin receptor antagonist [ERA], phosphodiesterase type 5 inhibitor [PDE5-I], soluble guanylate cyclase [sGC] stimulator)
- World Health Organization (WHO) Functional Class (FC) (Class I, Class II, or Class III)
- Baseline 6MWD (<350 meters or  $\ge$ 350 meters).

#### 9.3 PREMATURE DISCONTINUATION AND MISSING DATA

Subjects may not complete the Treatment Phase or the Optional Extension Phase for the following reasons: death, disease progression, adverse event, lost to follow-up, protocol violation, withdrawal of consent, or termination of the study by the Sponsor. All available data from all subjects in the Safety Population will be used as detailed in this analysis plan.

#### 9.4 MULTIPLE COMPARISONS AND MULTIPLICITY

No adjustments for multiplicity will be done.

#### 9.5 DERIVED AND TRANSFORMED DATA

#### 9.5.1 Baseline

In general, Baseline for any assessment will be defined as the measurement obtained at the Baseline Visit. If the assessment is not collected at the Baseline Visit, the last measurement prior to the first TreT dose will be defined as Baseline.

# 9.5.2 QT Intervals

Adjustments to the QT intervals will be calculated as shown in Table 9-1.

**Table 9-1** Adjustments to QT Intervals

Parameter	Formula
QTc (Bazett)	$= QT/\sqrt{60/HR}$
QTc (Fridericia)	$= QT/\sqrt[3]{60/HR}$

Abbreviations: HR, heart rate; QTc, QT interval corrected for heart rate.

#### 9.6 ASSESSMENT WINDOWS

For any data summarized by scheduled visit, an analysis visit window will be used. In the protocol, the visit window for the Week 3 Visit and the End of Study Visit is  $\pm 3$  days. The visit window for the Optional Extension Phase Visits is  $\pm 5$  days. In order to allow slotting of discontinuation visits and visits outside the planned schedule, the visit windows have been expanded for analysis purposes. The scheduled visits, as recorded on the eCRFs, and the corresponding target days and study day intervals are specified in Table 9-2. The analysis visit will be derived based on the information specified in Table 9-2.

**Table 9-2** Assessment Windows for Scheduled Visits

Visit	Target Study Day	Study Day Interval	
ECGs			
Baseline	1 Study Day ≤1 (prior to the date of the first dose)		
End of Study Visit		Last assessment after Study Day 1	
	PC	Q-ITD	
Baseline	1	Study Day ≤1 (prior to the date of the first dose)	
Week 3	22	1< Study Day ≤ Last assessment day during Treatment Phase	
End of Study Visit		Last assessment after Study Day 1	
	PAH-S	YMPACT	
Baseline	1	Study Day ≤1 (prior to date of the first dose)	
Week 3	22	1< Study Day ≤ Last assessment day during Treatment Phase	
Week 11	78	Any assessment during Optional Extension Phase	
End of Study Visit		Last assessment after Study Day 1	
Clini	cal laboratory asses	ssments, vital signs, 6MWT	
Baseline	1	Study Day ≤1 (prior to date of the first dose)	
Week 3	22	1< Study Day ≤ Last assessment day during Treatment Phase	
Week 11	78	Last assessment day during Treatment Phase < Study Day ≤106	
Subsequent weeks (every 8 weeks after Week 11)	Week*7+1	Target Study Day-28 < Study Day ≤ Target Study Day+28 or last assessment day during the Optional Extension Phase for final visit	
End of Study Visit		Last assessment in the study	

Abbreviations: 6MWT, 6-Minute Walk Test; ECG, electrocardiogram; PAH-SYMPACT, Pulmonary Arterial Hypertension-Symptoms and Impact; PQ-ITD, Preference Questionnaire for Inhaled Treprostinil Devices; \*, times. Note: Study Day = (Assessment Date) – (First Dosing Date) +1

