7.5 END OF STUDY VISIT AND/OR EARLY TERMINATION VISIT

If a subject elects to discontinue TreT at the end of the Treatment Phase, an End of Study Visit must be completed within 2 weeks (±3 days). If a subject is discontinued from the study prematurely, an Early Termination Visit should be completed as soon as possible. Subjects who permanently discontinue TreT are encouraged to undergo premature termination assessments prior to discontinuing TreT or as close as possible to the last dose of TreT. The following activities will be performed:

- Administration of PQ-ITD (TreT assessment; only for subjects that discontinue during the 3-week Treatment Phase)
- Administration of PAH-SYMPACT Questionnaire
- Physical examination
- Vital signs (following at least 5 minutes of rest), including weight, RR, HR, SBP, and DBP
- Urine pregnancy test for WOCBP
- Blood draws for clinical laboratory parameters
- 12-lead ECG (following at least 5 minutes of rest)
- Peak 6MWT (should be conducted between 10 to 60 minutes after the most recent dose and following at least 10 minutes of rest [sitting])

- Dosing diary/TreT accountability
- AE assessment
- Concomitant medications

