# Multiple Evaluations Within the Same Analysis Window

After all the observations have been slotted based on the table above, if there are multiple valid observations for an assessment within an assigned analysis visit window, only 1 of these observations will be used for summary statistics and analyses. The observation to be used is determined using the following hierarchy (in decreasing order):

- The observation closest to the target study day.
- The later observation if 2 observations are equally close to the target study day.

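### The SAP's Week 11 window for labs, vital signs and 6MWT lacks an extension-phase condition, so read literally it also takes in off-TreT End of Study records

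*SAP*

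**What the plan says.** SAP 9.6 makes Table 9-2 the operative slotting rule: "The analysis visit will be derived based on the information specified in Table 9-2". For labs, vital signs and 6MWT the relevant rows are:

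- Week 11, target Day 78: "Last assessment day during Treatment Phase < Study Day ≤106".
- Later extension visits: "Target Study Day-28 < Study Day ≤ Target Study Day+28", with an allowance for the final visit.
- End of Study: the last assessment the subject has in the study.

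For PAH-SYMPACT, the Week 11 row reads "Any assessment during Optional Extension Phase".

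When several records share a window, the first rule is to take "The observation closest to the target study day".

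SAP 3 fixes the extent of the Treatment Phase: "The Treatment Phase consists of 2 study visits to the clinic separated by 3 weeks of treatment with TreT". For a subject who does not enter the extension, it says "he/she must discontinue TreT, may resume Tyvaso therapy, and must return to the clinic 2 weeks after TreT discontinuation". Protocol 7.5 words the timing a little differently, asking for the visit within two weeks with a three-day tolerance. Labs, vital signs and a 6MWT are all done at that visit (Protocol Table 3-1 and 7.5).

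**The concern.** The Week 11 row for labs, vital signs and 6MWT is bounded below only by the subject's last Treatment Phase assessment. It has neither the phase condition of the PAH-SYMPACT row nor the 28-day lower bound of the later rows. Either one would keep out a visit made about two weeks after TreT was stopped by someone who never entered the extension.

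Evaluating long-term safety and tolerability of TreT in the extension is a secondary objective. If the row is programmed as written, the Week 11 lab summaries and shift tables could mix subjects taking TreT in the extension with subjects who are off TreT and possibly back on Tyvaso.

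**Working it through.** **Inputs.** Table 9-2 targets and intervals (SAP 9.6). Week 3 target Day 22 (SAP) or Day 21 (Protocol Table 3-1). Tolerance of ±3 days for both Week 3 and End of Study (Protocol Table 3-1 footnotes). End of Study 2 weeks after stopping TreT (SAP 3). Assumption: the last TreT dose is on the day of the Week 3 Visit.

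**Step 1: reproduce the plan's own figures.** Target = week × 7 + 1 = 11 × 7 + 1 = Day 78. Upper bound = 78 + 28 = Day 106. The Week 19 window opens after (19 × 7 + 1) − 28 = 134 − 28 = 106, so the two windows meet without overlap. The stated 78 and 106 are reproduced.

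**Step 2: place a decliner's End of Study Visit.**

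| Timing rule | Earliest day | Latest day | Days before Day 78 |
|---|---|---|---|
| SAP 3, Week 3 = Day 22 | 19 + 11 = 30 | 25 + 17 = 42 | 36 to 48 |
| SAP 3, Week 3 = Day 21 | 18 + 11 = 29 | 24 + 17 = 41 | 37 to 49 |
| Protocol 7.5, Week 3 = Day 22 | 19 + 1 = 20 | 25 + 17 = 42 | 36 to 58 |

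**Step 3: test against the Week 11 row.** Under the SAP 3 timing there are 2 Week 3 conventions × 7 Week 3 days × 7 gaps (11 to 17 days) = 98 combinations. The End of Study day is always later than the Week 3 day and never later than Day 42, so all 98 meet the Week 11 interval. The Protocol 7.5 timing also stays inside it.

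**Step 4: does another rule remove the record?** The closest-to-target rule only chooses among records within one window, and a decliner has no other record there. The End of Study row also takes the record but is not stated to be exclusive. SAP 8 defines only the Safety Population, so no extension population filters it out. The record is therefore slotted twice, to Week 11 and to End of Study.

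**Step 5: apply the safeguards used elsewhere in the table.** With the PAH-SYMPACT condition, 0 of 98 combinations slot to Week 11. With a 28-day lower bound (Study Day > 78 − 28 = 50), also 0 of 98, since the latest is Day 42. On-schedule Week 11 extension visits (78 ± 5, Day 73 to 83) still qualify under either.

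**Step 6: share of the Week 11 lab sample, for illustration only.** The number of decliners, d, is not given. Assume N = 45 (the planned size) and that every decliner has End of Study labs. Let a be the fraction of extension subjects with a Week 11 value. Share = d / (d + a(45 − d)).

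| d | a = 1.0 | a = 0.7 |
|---|---|---|
| 0 | 0% | 0% |
| 1 | 1/45 = 2.2% | 1/31.8 = 3.1% |
| 3 | 3/45 = 6.7% | 3/32.4 = 9.3% |
| 5 | 5/45 = 11.1% | 5/33 = 15.2% |
| 9 | 9/45 = 20.0% | 9/34.2 = 26.3% |

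The values of d and the 70% are assumptions. SAP 1.2.1 says only that extension visits were missed during site closures.

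**The case against.** **By-phase summaries.** SAP 9 says data will in general be summarised separately for each phase, and this covers labs too. SAP 11.1 and 12.4 refer to visits during each phase for 6MWD and vital signs, and the list of tables has a separate extension 6MWD table. An analyst who follows this could leave decliners out of any extension Week 11 cell. This stands as mitigation, more strongly for 6MWD and vital signs than for labs, where SAP 12.3.1 speaks only of each visit. The absence of a phase in the lab table titles proves little, since the vital signs title has none either. But the by-phase statement governs presentation. It does not change what Table 9-2 slots to Week 11.

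**The visit may belong to the Treatment Phase.** SAP 3 describes it in the Treatment Phase paragraph, and Protocol 3.6 puts the mandatory part at a minimum of 5 weeks, that is 3 + 2. On that reading the record falls in the Week 3 window and loses to the actual Week 3 value in all 98 combinations, so the problem disappears. The two-visit definition in SAP 3 and the separate End of Study column in Protocol Table 3-1 count against it. That two readings exist is itself a reason to state the condition.

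**The wide windows are deliberate.** SAP 9.6 expands them to slot discontinuation and off-schedule visits. That is so, but nothing there says that a planned post-TreT visit by someone who never entered the extension should represent Week 11.

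**Materiality.** Lab summaries are descriptive with no decision rule, all lab records are listed, and clinically significant lab abnormalities are reported as AEs. This stands and keeps the point minor.

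**Conclusion.** The Week 11 row is incomplete. It rests on a literal reading of Table 9-2 with the Treatment Phase taken as the Baseline and Week 3 visits. On that reading a decliner's off-TreT record counts at Week 11 in addition to End of Study. Labs are the clearest exposure. The effect is limited to descriptive Week 11 by-visit and shift summaries and is zero if no subject declines. Neither the number affected nor the size or direction of any shift in values can be derived from the documents. Severity is minor.

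Three stronger conclusions that a reader might draw are not supported:

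- That the record is lost from End of Study. It keeps its place in that row.
- That 6MWD, including a Week 11 paired t-test, is distorted. The phase wording in SAP 11.1 gives good reason to exclude decliners. Although 11.1 mentions a test at each week, the list of tables names an analysis only in the Treatment Phase 6MWD table, so an effect on a Week 11 test is not established.
- That the long-term safety evaluation as a whole is compromised. AE summaries do not use Table 9-2, and the listings are unaffected.

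**What to change.** In Table 9-2, limit the Week 11 row for labs, vital signs and 6MWT to assessments during the Optional Extension Phase, as the PAH-SYMPACT Week 11 row already does. Decliners' End of Study records then go only to the existing End of Study row. Identify them there as post-TreT values, because that row also holds the last assessments of extension subjects. The later rows need no change for this purpose.

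The cost is one condition in one row, the matching programming and a label; no new data are needed. The downside is slightly fewer records at Week 11. A Day 50 lower bound would also keep decliners out, but it would leave early-termination visits of extension subjects on or before Day 50 without a by-week slot, so the phase condition is preferable.

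### SAP Table 9-2: End of Study for laboratory values, vital signs and 6MWT can return a Baseline value, and the End of Study rows mix on-TreT with post-TreT values

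*SAP*

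**What the plan says.** Table 9-2 in SAP section 9.6 has four blocks. For ECG, PQ-ITD and PAH-SYMPACT, End of Study is "Last assessment after Study Day 1". For laboratory values, vital signs and 6MWT it is "Last assessment in the study", with no target day, no lower day limit and no dosing condition. Baseline in that same block is "Study Day ≤1 (prior to date of the first dose").

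The table decides the visit, not the eCRF label: "The analysis visit will be derived based on the information specified in Table 9-2". Where several observations share a window, the first criterion is "The observation closest to the target study day", which cannot operate on a row without a target day. The Safety Population (SAP section 8) needs one TreT dose and no later assessment. SAP section 9.3 uses all available data from it.

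On treatment state, SAP section 3 says of a subject who declines the extension that "he/she must discontinue TreT, may resume Tyvaso therapy, and must return to the clinic 2 weeks after TreT discontinuation". Extension subjects stay on TreT. Protocol section 7.5 encourages subjects who stop permanently to be assessed before, or close to, their last dose. It also lists laboratory tests, vital signs, ECG and a walk test at this visit: "Peak 6MWT (should be conducted between 10 to 60 minutes after the most recent dose".

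On timing, SAP section 6 plans an analysis once all subjects finish the Treatment Phase, and adds: "Any available data from the Optional Extension Phase will also be analyzed at this time".

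**The concern.** Two things looked wrong. First, one block of the table lacks a safeguard that the other three have, and nothing elsewhere in the SAP clearly supplies it. A subject with no follow-up data would then appear in a follow-up row, with a laboratory change of exactly zero.

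Second, the End of Study label covers different states: two weeks off TreT and possibly back on Tyvaso, still on TreT in the extension, or at early termination near the last dose. A pooled summary of these describes neither the effect of TreT nor the state after stopping it. For a decliner, the most recent dose before the End of Study walk is either Tyvaso or a TreT dose about two weeks old, so that walk is not a peak TreT walk.

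Safety and tolerability is the primary objective, and laboratory values, vital signs and ECG are among its endpoints. A last row in a safety table is easily read as the final on-treatment result.

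**Working it through.** The plan states no figure for this point, and the sample size of 45 has no power basis, so there is nothing to reproduce. The check applies the rule literally.

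**Step 1. Four illustrative subject paths.** Day 36 is the SAP's Week 3 target of Day 22 plus 14 days. Day 134 is Week 19 (19 × 7 + 1).

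| Path | As written | Adding the Day 1 condition | Also requiring on TreT |
|---|---|---|---|
| A. Dosed on Day 1, no later test | Day 1 Baseline, change 0 | Missing | Missing |
| B. Week 3 on Day 22, declines extension, returns Day 36 | Day 36, off TreT | Day 36, off TreT | Day 22 |
| C. Extension, last visit Day 134 on TreT | Day 134 | Day 134 | Day 134 |
| D. Early termination Day 10, still on TreT | Day 10 | Day 10 | Day 10 |

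The Day 1 condition repairs path A only. Path B needs a separate rule.

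With ±3 days on both visits, and TreT stopped at the Week 3 Visit, the decliner's value falls between Day 22 − 3 + 14 − 3 = 30 and Day 22 + 3 + 14 + 3 = 42. Counting from the protocol's Day 21 gives Day 29 to 41.

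**Step 2. Where path A reaches.**
- Laboratory values (SAP 12.3.1): values and changes are summarised at each visit with no post-Baseline limit, so A enters both. The shift summary speaks of values that came subsequently and, on its natural reading, leaves A out.
- Vital signs (SAP 12.4): changes are restricted to post-Baseline assessments, so A enters the values only.
- 6MWD (SAP 11.1): summaries are by visit within the two phases and End of Study is not named. A enters only if such a row is displayed. The paired t-test is by week.

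**Step 3. Where the mixing of states reaches.**
- All four rows lack an on-TreT condition; this is not peculiar to the laboratory block.
- ECG: the only scheduled recordings are at Baseline and End of Study or Early Termination (Protocol 3.3.2.4). The row therefore pools decliners two weeks off TreT with early terminators on or near TreT.
- PAH-SYMPACT: SAP 11.3 names End of Study. The last assessment may be a decliner's post-TreT visit, an early termination, or Week 11 on TreT.
- PQ-ITD: Protocol 7.5 gives it at this visit only to subjects who stop within the 3 weeks, so decliners add no post-TreT value.

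**Step 4. Possible composition, on assumed counts.** The documents count neither kind of subject. Suppose all 45 planned subjects have an End of Study entry.
- With k Baseline-only subjects, the share is k/45 and the mean change is (45 − k)/45 times the mean of the others. For k = 1, 3, 5 the shares are 2.2%, 6.7%, 11.1% and the multipliers 0.978, 0.933, 0.889.
- With m decliners, the off-TreT share is m/45. For m = 5, 10, 20 it is 11.1%, 22.2%, 44.4%. This is a share of the row, not a bias.

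**The case against.** The best defence is that End of Study is a protocol-defined visit which the SAP never calls an on-treatment endpoint. On-TreT results already appear under Week 3, Week 11 and later weeks. SAP section 9 summarises data separately for each phase, and the 6MWD tables are titled by phase. The 6MWT listing shows the last TreT or Tyvaso dose and the hours since it. Path A should also be rare, because the protocol calls for an Early Termination Visit that includes these assessments.

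Much of this stands. Vital-sign changes are protected, the laboratory shift table probably is, and 6MWD is exposed only if the row is shown. No planned test uses End of Study.

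It does not remove the point. The row is defined over the whole study, and the laboratory and vital-sign tables in the SAP's table list are not split by phase. Even within the Treatment Phase, early terminators and decliners are in different states. Rare is not excluded: the plan should not return a Baseline value as follow-up for any subject.

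A reader might infer that the 3 subjects without Week 3 PK (SAP 1.2.1) are Baseline-only cases. The SAP says only that they lacked PK, not that they lacked laboratory, vital-sign or walk data. Nor do the documents show that Baseline-only subjects would be the intolerant ones.

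**Conclusion.** The point holds as a defect in descriptive summaries. For laboratory values, vital signs and 6MWT the rule as written can report Baseline as End of Study, within the limits in Step 2. All End of Study rows lack a treatment condition, and the resulting mixture matters for those three plus ECG and PAH-SYMPACT. At the Treatment Phase analysis, the laboratory and vital-sign entry for an ongoing extension subject is only the latest available visit.

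Neither the size nor the direction of the overall effect can be derived. A reader might infer that the row shows a fixed fraction of the on-TreT change, namely one minus the off-TreT share and the Baseline-only share. The documents do not support this. Both shares are uncounted, and the formula needs off-TreT subjects to be back at Baseline with the remaining subjects sharing one on-TreT change. Baseline was measured on stable Tyvaso, so a subject taking neither product need not be at Baseline. Carried Baseline zeros alone shrink a mean change by arithmetic, but the off-TreT part has no derivable sign. A further inference, that the 6MWD test is compromised, also fails because that test is by week.

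**What to change.** 1. In the laboratory, vital signs and 6MWT block, replace the End of Study interval by "Last assessment after Study Day 1", as in the other blocks.
2. For laboratory values, vital signs, 6MWT, ECG and PAH-SYMPACT, summarise two rows separately. The first is a last on-TreT value: the last assessment after the first TreT dose and on or before the date of the last TreT dose. The second is a post-TreT value: an assessment after the last TreT dose, covering late Early Termination Visits as well as subjects who decline the extension.
3. At the Treatment Phase analysis, label the entries of ongoing extension subjects as last available value.

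The cost is SAP wording and programming. The date of the last TreT dose is already in the planned listings (SAP 10.1 and 12.1), so no new data are needed. Each split row will hold fewer subjects. This will show most for ECG, where no Week 3 recording is scheduled and decliners will have only a post-TreT value.
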